1.1.2.2. Overall Design

Substudy B

Substudy B will be conducted as a Phase 1b, parallel-group, randomized, observer-blinded substudy of RSVpreF and a nucleoside-modified RNA vaccine (qIRV) against RSV and influenza administered as a combined vaccine in a 1.0-mL formulation and when administered in a 0.5-mL formulation.

Healthy adults ≥50 years of age will be randomized 1:1 to either Group 1: combination (RSVpreF + qIRV) 1.0-mL formulation; or Group 2: combination (RSVpreF + qIRV) 0.5-mL formulation. Randomization will be stratified by 6 age/sex groups (female 50-64, female 65-79, and female ≥80 years; male 50-64, male 65-79, and male ≥80 years) within the study site. Approximately 100 participants will be randomized within the 50- through 64-year-old group, and 100 participants ≥65 years of age will be randomized. Study groups, blood draws, and safety assessment timings are presented below.

Age Group N=200	Study Group Randomization 1:1 within each age cohort	Subjects per Group	Sentinel Cohort Visit B101 (Vaccination, Day 1)	Expanded Enrollment Visit B101 (Vaccination, Day 1)	Visit B102 (Follow-up, Day 28 – Day 35)
	Group 1 RSVpreF + qIRV 1.0-mL formulation*	10	RSVpreF + qIRV 1.0 mL		blood draw
50-64		40		RSVpreF + qIRV 1.0 mL	•
years n=100	Group 2 RSVpreF + qIRV 0.5-mL formulation**	10	RSVpreF + qIRV 0.5 mL		blood draw
		40		RSVpreF + qIRV 0.5 mL	•
≥65 years	Group 1 RSVpreF + qIRV 1.0-mL formulation*	50		RSVpreF + qIRV 1.0 mL	blood draw
n=100	Group 2 RSVpreF + qIRV 0.5-mL formulation**	50		RSVpreF + qIRV 0.5 mL	blood draw
Safety Asse	ssments				
	Local reactions and systemic events Days 1 through 7 Days 1 through 7				
AEs and AESIs			Consent through study completion		48 hours
	SAEs Consent through study completion				
*Group 1: 1.0-mL formulation: CCI **Group 2: 0.5-mL formulation					

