C3671013 is an ongoing Phase 3, multicenter, randomized, double-blind, placebo-controlled study to assess the safety, immunogenicity, and efficacy of Pfizer's RSVpreF in prevention of RSV-associated LRTI in adults 60 years of age and older. Both healthy adults and adults with stable chronic cardiopulmonary conditions are included. Approximately 10% of participants with stable chronic cardiopulmonary conditions such as COPD, asthma, or CHF are being enrolled. The study enrolled over 37,000 participants, randomized to receive RSVpreF or placebo in a 1:1 ratio. This is an event-driven study with a target of 59 first episodes of evaluable RSV-associated LRTI cases. Interim analysis results in August 2022 showed protection against LRTI-RSV defined by 2 or more symptoms demonstrated vaccine efficacy. 66.7%. Vaccine efficacy of 85.7% was observed in participants with a more severe disease primary endpoint of LRTI-RSV defined by analysis of 3 or more RSV-associated symptoms. The vaccine was well tolerated, with no safety concerns.

C3671006 is a Phase 3, multicenter, parallel-group, placebo-controlled, randomized, double-blind study. 1403 healthy adults ≥65 years of age were randomized 1:1 to either a coadministration group or a sequential-administration group. The intention of this study was to demonstrate that the immune responses generated when a 120-µg RSVpreF dose was coadministered with SIIV were noninferior to the immune responses when these products were administered 4 weeks apart. The safety and tolerability of RSVpreF were also examined. Results demonstrated noninferiority of the RSVpreF and SIIV immune responses when RSVpreF was coadministered with SIIV. The results of this study support the acceptability of coadministration of RSVpreF and SIIV in an older adult population.

RSVpreF is also being studied in the maternal program, which includes Phase 2b and Phase 3 studies in pregnant women and a Phase 2b study in nonpregnant women. Details of each of these studies are provided in the RSVpreF IB.

2.2.3.2. qIRV

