10.10.7. Substudy B Population

10.10.7.1. Inclusion Criteria

Participants must meet the following inclusion criteria to be eligible for enrollment into Substudy B:

Age and Sex:

Participants ≥50 years of age at study enrollment.

Refer to Section 10.4 for reproductive criteria for male (Section 10.4.1) and female (Section 10.4.2) participants.

Disease Characteristics:

Not applicable.

Other Inclusion Criteria:

- Participants who are willing and able to comply with all scheduled visits, investigational plan, laboratory tests, lifestyle considerations, and other study procedures.
- Healthy participants who are determined by medical history, physical examination (if required), and clinical judgment of the investigator to be eligible for inclusion in the study.

Note: Healthy participants with preexisting stable disease, defined as disease not requiring significant change in therapy or hospitalization for worsening disease during the 6 weeks before enrollment, can be included. Specific criteria for participants with known stable infection with HIV, HCV, or HBV can be found in Section 10.11.

- Capable of giving and having signed the informed consent as described in the protocol, which includes complying with the requirements and restrictions listed in the ICD and in this protocol.
- Receipt of licensed influenza vaccination for the 2022-2023 northern hemisphere season or 2022 southern hemisphere season >180 days before study intervention administration.

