2.3.2. Substudy B

Substudy B is designed to evaluate the safety, tolerability, and immunogenicity of RSVpreF and a modified RNA vaccine (qIRV) against RSV and influenza when administered as a combined vaccine in a 1.0-mL formulation and a 0.5-mL formulation.

This 2-visit study will be conducted as a Phase 1b, parallel-group, randomized, placebo-controlled, observer-blinded substudy.

Approximately 200 healthy participants (n=100 per group) will be enrolled in Substudy B.

Note: "Enrolled" means a participant's agreement to participate in a clinical study following completion of the informed consent process.

Healthy adults \geq 50 years of age will be randomized 1:1 to either:

- Group 1: combination (RSVpreF + qIRV) 1.0-mL formulation or
- Group 2: combination (RSVpreF + qIRV) 0.5-mL formulation.

Participants will be randomized by age/sex strata. Randomization will be stratified at the study site by 6 age/sex groups so that approximately 100 participants will be 50 through 64 years of age and 100 will be \geq 65 years of age, in addition to having balanced sex distribution between vaccine groups. These groups are as follows:

- Females 50 through 64 years of age
- Females 65 through 79 years of age
- Females ≥ 80 years of age
- Males 50 through 64 years of age
- Males 65 through 79 years of age
- Males ≥ 80 years of age

Blood will be collected prior to vaccination and at the final study visit.

Local reactions and systemic events occurring within 7 days after vaccination will be recorded in an e-diary device or smartphone application.

AEs and SAEs will be collected from the signing of informed consent through study completion.

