6.5. Safety Summaries and Analyses

6.5.1. Adverse Events

For both SSA and SSB: For all of the AEs categorized in Section 3.1.3.3 and Section 3.1.3.4, each individual AE including SAE after vaccination will be categorized by the MedDRA PT and descriptively summarized with count, percentage, and 95% CI for vaccine group.

For Tier 1 events, the 2-sided 95% CIs for the difference in the percentage of participants reporting the events between the RSVpreF contained group and the control group will be calculated using the test statistic proposed by Miettinen and Nurminen³; in addition, the asymptotic p-values will also be presented for the difference in the percentage of participants reporting the events, based on the same test statistic and under the assumption that the test statistic is asymptotically normally distributed.

Because all participants enrolled in this study are expected to receive either RSVpreF or (RSVpreF+qIRV), there is no control in this study. Therefore, the intervention group will be all participants who received (RSVpreF+qIRV) or RSVpreF from both SSA and SSB, and the control group will be from RSVpreF pivotal Phase 3 study (C3671013) who received placebo only. The count for each Tier 1 event and denominator from C3671013 placebo group will be provided in this Tier 1 AE analysis.

It should be recognized that most studies are not designed to reliably demonstrate a causal relationship between the use of a pharmaceutical product and an AE or a group of AEs. Except for selecting events in unique situations, studies do not employ formal adjudication procedures for the purpose of event classification. As such, safety analysis is generally considered an exploratory analysis and its purpose is to generate hypotheses for further investigation.

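### The Tier 1 safety pool starts at age 50 but its external placebo control starts at age 60, and no age restriction or adjustment is stated, so the comparison is open to age confounding of unknown net direction

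*SAP*

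**What the plan says.** SAP 3.6.1 names Guillain-Barre syndrome, atrial fibrillation and polyneuropathy as Tier 1 events for RSVpreF. SAP 6.5.1 plans a between-group difference in percentages for them, with a two-sided 95% Miettinen-Nurminen interval and an asymptotic p-value. Since everyone in the study is expected to receive RSVpreF in some form, the SAP borrows a control. On one side, "the intervention group will be all participants who received (RSVpreF+qIRV) or RSVpreF from both SSA and SSB"; on the other, "the control group will be from RSVpreF pivotal Phase 3 study (C3671013) who received placebo only". The section states no age limit, stratification or standardization.

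The two sides have different age floors. Protocol 2.2.3.1 describes C3671013 as a study "in prevention of RSV-associated LRTI in adults 60 years of age and older". Substudy A also starts at 60. The Substudy B inclusion criterion (Protocol 10.10.7.1) is "Participants ≥50 years of age at study enrollment", and Protocol 1.1.2.2 adds "Approximately 100 participants will be randomized within the 50- through 64-year-old group". The documents do not say how many of those 100 will be under 60.

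**The concern.** With an external, non-randomized control, comparability rests entirely on how the two groups are defined. Here one age stratum exists only on the intervention side. If the background rate of a Tier 1 event differs between people in their fifties and people aged 60 and over, part of the estimated difference reflects age rather than vaccine.

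These are the only adverse events for which SAP 6.5.1 plans a between-group difference and a p-value, and the planned output would not show a reader that the age ranges differ. Elsewhere the sponsor does treat age as relevant: Substudy B is stratified by age and sex, and its adverse events are derived for 50-64, 65+ and 50+ years. Those bands do not solve this problem, because 50-64 straddles the control's floor of 60.

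**Working it through.** The SAP gives no rate, margin or power for the Tier 1 comparison, so there is no figure of its own to reproduce.

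**Inputs from the documents**
- Substudy A: about 250 participants, all aged 60 or over, with at most 40 aged 60-64 (Protocol 10.9.6.1).
- Substudy B: "Approximately 200 healthy participants (n=100 per group) will be enrolled in Substudy B", split about 100 aged 50-64 and 100 aged 65 or over (Protocol 10.10.6.1).
- Planned pool: 250 + 200 = 450.
- Control: "The study enrolled over 37,000 participants, randomized to receive RSVpreF or placebo in a 1:1 ratio" (Protocol 2.2.3.1), so about 37,000 / 2 = 18,500 placebo recipients.

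**Assumptions, because the documents are silent**
- p0, the background event rate in the control: 0.01% to 1%.
- r, the rate at 50-59 relative to the older reference: 0 to 1.
- k, the rate at 65 and over relative to 60-64: 1.25 to 3.

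**Step 1. Share of the pool below the control's age floor**
- At most 100/450 = 22.2%.
- With ages 50-64 spread evenly: 100 × 10/15 ≈ 67, and 67/450 ≈ 15%.

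**Step 2. Contribution of ages 50-59 alone**

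Suppose recipients aged 60 and over match the control, and let f be the share under 60. With no vaccine effect, the expected risk difference is −p0 × f × (1 − r). The extreme case is f = 22.2% and r = 0. The intervals below are Miettinen-Nurminen 95% intervals for 450 against 18,500 at expected counts, with no age bias.

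| Assumed p0 | Extreme shift (percentage points) | 95% interval (percentage points) |
|---|---|---|
| 0.01% | −0.002 | −0.03 to +0.86 |
| 0.1% | −0.02 | −0.11 to +0.94 |
| 0.5% | −0.11 | −0.38 to +1.19 |
| 1% | −0.22 | −0.62 to +1.42 |

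With f = 14.8% and r = 0.5 at p0 = 1%, the shift is −0.07. With r = 1 it is zero.

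**Step 3. Net direction once the age mix above 60 is allowed to differ**

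At least 450 − 100 − 40 = 310 of the pool (69%) are 65 or over. With the cap filled and an even spread, the pool is about 67 aged 50-59, 73 aged 60-64 and 310 aged 65 or over. Setting the rate at 60-64 to 1, its average is I = (67r + 73 + 310k)/450. If a share q of the control is aged 60-64, the control average is q + (1 − q)k. The two are equal at q = (k − I)/(k − 1). Below that q the pool has the lower background rate; above it, the higher.

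For r = 0.5 and k = 2, I ≈ 1.615 and q ≈ 38%. Over r = 0 to 0.75 and k = 1.25 to 3, the break-even share runs from 33% to 90%. If all 100 were under 60, it would run from 34% to above 100%, so in some scenarios the direction could not reverse. The documents do not give q.

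**Step 4. Would an age filter alone be enough?**

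Take r = 0.5, k = 2 and q = 38%.
- Control average: 0.38 + 0.62 × 2 = 1.62.
- Full pool: (33.5 + 73 + 620)/450 = 1.61, ratio about 1.00.
- Pool restricted to 60 and over: (73 + 620)/383 = 1.81, ratio 1.12.

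In this scenario the filter alone turns a balanced comparison into one that leans toward harm. Comparison within age bands removes that imbalance.

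**Step 5. Precision cost of restriction**

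The upper 97.5% bound with zero events is 1 − 0.025^(1/n): 0.82% at n = 450, 0.96% at n = 383, and 1.05% at n = 350 (all 100 under 60).

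**The case against.** The strongest reply is that the mismatch hardly matters. SAP 6.5.1 calls safety analysis generally exploratory and meant to generate hypotheses, and no margin or decision rule attaches to the p-value. At a 0.1% rate the whole pool expects 0.45 events, so sampling error dominates. Age is also only one difference from a cross-study control: about 10% of C3671013 participants have stable chronic cardiopulmonary conditions, and an age fix leaves that untouched. Substudy B adverse events are shown by age group anyway. SAP 6.3 on subset analyses is blacked out, so whether it reaches the Tier 1 comparison cannot be judged.

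All of this lowers the stakes, and it stands to that extent. It does not justify keeping, in an unadjusted contrast, a stratum that the control cannot contain.

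A reader might also infer something stronger: that including people in their fifties dilutes the risk difference toward no harm. The documents do not support that. It needs Tier 1 rates that are lower at 50-59, and the documents give neither rates nor an age gradient for any of the three events. It also needs a pool with a lower background risk than the control overall. The Substudy A cap on ages 60-64 pulls the other way, and the control's age mix is not given. What can be said is narrower: if risk is lower at 50-59, that stratum's own contribution is downward, but the net bias can go either way.

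**Conclusion.** The point holds as an age mismatch with no stated restriction or adjustment. That rests directly on SAP 6.5.1, Protocol 2.2.3.1 and Protocol 10.10.7.1, and needs no assumption beyond the planned enrolment. Up to about 22% of the pool has no counterpart in the control, or about 15% under an even spread of ages 50-64.

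The net direction is unknown. The part due to ages 50-59 is at most about 0.22 percentage points at an assumed 1% rate, if recipients aged 60 and over match the control and risk at 50-59 is no higher than above 60. The part due to the age mix above 60 cannot be bounded without the C3671013 age distribution. The change is worth making before the analysis because it is cheap, but the mismatch does not threaten the study's main conclusions.

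**What to change.** In SAP 6.5.1:

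1. Restrict the external Tier 1 comparison to recipients aged 60 or over at vaccination. SAP 3.5.2 already derives this age.
2. Obtain the C3671013 placebo counts and denominators by age band, for example 60-64, 65-79, and 80 and over, which follow the substudies' own randomization cut-points above 60. Compute the Miettinen-Nurminen difference stratified by those bands, with the stratum weights stated, or standardized to them. Restriction without this step is not enough (Step 4 of the working).
3. List Tier 1 events in participants aged 50-59 separately, outside the external comparison.
4. Show the all-ages unadjusted result as a supplement.

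The cost is SAP wording, one age filter and a request for age-banded control counts. The comparison loses some participants: about 383 instead of 450 under the even-spread assumption, which moves the zero-event upper 97.5% bound from 0.82% to 0.96%. No event goes unreported. Differences in health status from the external control remain and should be acknowledged when the result is presented.

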6.5.2. Myocarditis or Pericarditis

The variable derived in Section 3.5.3 will be summarized with count, percentage, and 95% CI by vaccine group only at Visit 1 for either Substudy A or Substudy B.

A listing for ECG and measurement of troponin for potential myocarditis/pericarditis evaluation will be provided. Symptoms, ECG results, troponin level, cardiac study results, cardiac function evaluation, and final diagnosis results will all be listed for any participants with signs and symptoms onset within 28 days after Vaccination 1.

7. INTERIM ANALYSES

No interim analysis is planned for either Substudy A or Substudy B.

7.1. Introduction

Not applicable.

7.2. Interim Analyses and Summaries

Not applicable.

